6.5 COSTS TO THE SUBJECT

Subjects will not incur any costs for participating.

6.6 PAYMENT FOR PARTICIPATION

Subjects will not be paid for participation.

6.7 RETURN OF INDIVIDUAL RESEARCH RESULTS / MANAGEMENT OF HEALTH FINDINGS

As part of this study, we may identify new health information. During the consent process, we will obtain permission to disclose this information to each subject's PCP. This will be done via a template letter that will be sent by the study staff by standard postage mail to the PCP summarizing performance on the various tests. If the subject declines to allow us to provide this information to their PCP, then the disclosure will not occur.

As part of the surveys in the ED or via phone, we may identify certain findings that require physician review. For the surveys completed in the ED, the findings will be reviewed with the treating physician. For the phone surveys, these findings will be reviewed by the physicians overseeing this study at either the Rochester or Madison sites and action will be taken as clinically appropriate.

As part of the CTI coaching, the coach may identify clinical issues. Then, he/she will coach the subject to call his/her PCP to obtain further guidance. If the subject is unable to do so, then the coach will call the patient's provider or 911 for direct ED transport. By using trained providers (paramedics) with extensive clinical knowledge and having continual physician availability by phone, this decision will be maximally supported.

7. SUBJECT WITHDRAWALS

All subjects will be advised in the written informed consent forms that they have the right to withdraw from the study at any time without prejudice. Withdrawal will only occur if the subject indicates that he / she no longer wishes to participate. For subjects who withdraw from the study, we will clarify the level of withdrawal. For those who wish their records to be fully expunged from the study, we will destroy all information except for the consent form, but add a note indicating the date and time of withdrawal. For those who wish to cease participating in the CTI program and follow up activities, we will request permission to retain them in the study and continue medical record review until the end of study chart review.

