The CTI aims to improve *patient activation*, which is measured as having the skills, knowledge, and motivation to participate as effective members of the care team.⁶⁷ We will use the Wallston Perceived Health Competency Scale.

Upon study exit, we will measure our *primary outcome, health care use* within 30 days of ED discharge, through survey and administrative data from both local health systems and the insurers. We will also measure the costs of health care as well as the CTI program.

We will check the Social Security Death Index for death within 30 days for all subjects.

If a subject *withdraws* during follow-up, we will clarify the level of withdrawal that the subject is requesting—cessation of subject contact or removal from the study. If the subject requests cessation of contact, we will continue to review the subject's medical record to obtain health care use (e.g., ED use) outcomes. If a subject is *admitted to a skilled nursing facility*, which occurs in less than 2% of ED patients discharged home, we will track that outcome and measure those costs, but we will not survey those subjects.

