12.2 PLANNED STATISTICAL ANALYSIS

Through the analytic methods used in Aims 2 and 3, we will assess differences between groups related to process outcome measures (Aim 2) and will assess the effectiveness and cost-effectiveness of the ED-to-home CTI (Aim 3). In Aim 4, we will identify predictors of repeat ED use among intervention group subjects. We will characterize of our study sample using descriptive statistics and corresponding measures of variation. We will assess for differences between groups at baseline despite randomization in key characteristics (e.g., demographics, comorbidities) using t-tests for continuous variables and Chi-square tests for categorical variables, using Fisher's exact test where appropriate. These comparisons will enable the identification of covariates to be controlled in our multivariable analyses. If distributional assumptions associated with a particular statistical procedure are violated, we will use appropriate transformations or non-parametric alternatives. Primary analyses will be performed under the intent-to-treat principle, keeping subjects in the group to which they were originally randomized, regardless of compliance or adherence to study procedures. We will conduct sensitivity analyses among subjects who complete all study procedures to evaluate the effect of the intervention among those who complete all study-related procedures. Hypothesis-driven comparisons will be made to control the family-wise type I error rate at 0.05 (two-sided) for the primary hypothesis.

Caregiver Subject Analysis: Although not an original aim of the study, we have obtained permission from the NIH and will perform a limited analysis of caregiver activation. This was only recently added to

the CTI. To compare the caregiver activation between the control and intervention groups, we will administer the FCAT. The FCAT will be scored as 1-6 points per question, for a score ranging from 10-60. We assume that 30% of participants will have caregivers with them, the average score will be 30, and we will look for a 5 point difference. Our sample size will allow a power of >0.8 for a t-test ($\alpha=0.05$).

Hyp 1A: More program participants will demonstrate understanding of their ED discharge instructions, red flags that indicate a worsening of their condition, and how to respond to the red flags three days after ED discharge.

Hyp 1B: More program participants will implement medication changes made in the ED within three days of ED discharge.

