2. The site PI designee (who must be a clinician with relevant expertise) will be notified to determine if the event is unexpected, related to participation in the research and places participants at a greater risk of physical or psychological harm than was previously known or recognized.
3. The overall PI will be notified without unblinding the PI.
4. The NIA and Independent Safety Officer will be notified within 1 business day of categorization.
5. The governing IRB will be notified within 1 business day if the SAE constitutes an UP and is immediately life-threatening or severely debilitating to other participants.
6. If it is unexpected, related, or possibly related, the other study investigators and sites will be notified promptly.
7. The PI will provide a final update to the NIA and Independent Safety Officer within 14 business days of the event for all SAE cases, unless the investigation is still ongoing.
8. The event will be discussed on the weekly study oversight call.

Grading Criteria

We will utilize the NIA approved grading criteria, as indicated on the event forms including:

Severity

- 1 = Mild- Awareness of signs or symptoms, but easily tolerated and are of minor irritant type causing no loss of time from normal activities. Symptoms do not require therapy or a medical evaluation; signs and symptoms are transient.
- 2 = Moderate- Events introduce a low level of inconvenience or concern to the participant and may interfere with daily activities, but are usually improved by simple therapeutic measures; moderate experiences may cause some interference with functioning
- 3 = Severe- Events interrupt the participant's normal daily activities and generally require systemic drug therapy or other treatment; they are usually incapacitating

Study Relatedness

- 1 = Definitely related- The adverse event is clearly related to the study procedure – i.e. an event that follows a reasonable temporal sequence from administration of the study intervention, follows a known or expected response pattern to the suspected intervention, that is confirmed by improvement on stopping and reappearance of the event on repeated exposure and that could not be reasonably explained by the known characteristics of the subject's clinical state.

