3.0 DATA AND SAFETY MONITORING

3.1 Frequency of Data and Safety Monitoring

This data safety and monitoring plan is commensurate with the risks as well as the size and complexity of the study. This plan outlines the appropriate oversight and monitoring of the conduct and progress of the study to ensure that important information that may affect the safety and welfare of subjects is collected, recognized, and acted upon quickly while still ensuring the validity and integrity of the data. This monitoring plan includes structured adverse event (AE) and serious adverse event (SAE) determination, monitoring and reporting systems with standardized protocols and forms for referring and/or treating study participants who experience adverse events. AEs will be reported to the NIA Program Officer and the Independent Safety Monitor. UP will be reported to the reviewing IRB in accordance with its reporting policies.

The Principal Investigator (PI) will be responsible for ensuring participants' safety on a daily basis. The Independent Safety Officer will act in an advisory capacity to the NIA to monitor participant safety, data collection and evaluate the progress of the study.

Section 1.2 includes the full details of AE and SAE collection and action.

From a quantitative standpoint, the following will occur:

1. A **monthly** report to the Independent Safety Officer and to the NIA Project officer will be sent for review to further monitor subject safety. This will include monthly and cumulative data to identify trends in the events between the intervention and control groups.
2. A cumulative data and safety monitoring annual report will be sent to the Independent Safety Officer, the NIA Project officer, and reviewing IRBs (at the time of continuing review).

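### Full expungement under section 7 makes no exception for the allocated arm or for adverse event records, so later by-arm safety tables and the intent-to-treat set can be incomplete

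*Combined protocol and SAP*

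**What the plan says.** Section 3.2 gives a withdrawing subject two levels to choose from: "cessation of subject contact or removal from the study". Section 7 sets out what each means.

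- Full expungement: "For those who wish their records to be fully expunged from the study, we will destroy all information except for the consent form". The only other thing kept on file is a record of when the subject withdrew.
- Stopping the program and follow-up only: "we will request permission to retain them in the study and continue medical record review until the end of study chart review".

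Three other parts of the plan depend on records that the first option removes.

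- Section 12.2 defines the primary analyses as intent-to-treat, "keeping subjects in the group to which they were originally randomized, regardless of compliance or adherence to study procedures".
- Appendix A, section 3.1 requires a monthly report to the Independent Safety Officer and the NIA: "This will include monthly and cumulative data to identify trends in the events between the intervention and control groups". Template Tables 2 and 3 and Listing 1 are laid out separately for each group.
- Appendix A, section 1.2 says of SAEs: "The NIA and Independent Safety Officer will be notified within 1 business day of categorization". A final update is due within 14 business days of the event.

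**The concern.** The expungement rule is absolute. It covers data already collected, and it operates after the subject has been told the allocation (section 5.2). A request can therefore follow from what happened to the subject. Only the intervention arm has a home visit, coach calls and the in-home exposure to mandatory reporting described in section 9.1, so requests could plausibly differ between arms.

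The safety record is at stake first. A subject could have an SAE, ask to be expunged while it is under investigation, and leave the study with no source file for an event already notified. The analysis is at stake second. A randomised subject whose arm has been destroyed cannot be placed in either group, and the loss cannot be described by arm.

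**Working it through.** **What survives an expungement.** Consent and the baseline survey precede randomisation (sections 5.1 and 5.2), so the consent form cannot show the arm. The added note holds a date and a time. Nothing that section 7 keeps identifies the arm, the outcome or any event. I found no exemption in sections 3.2, 7, 8, 10 or 12, or in Appendix A.

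**Set against the rest of the plan.**

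1. *Intent-to-treat (12.2).* Without the arm, the subject cannot be analysed as randomised.
2. *Cumulative safety reporting (Appendix A, 3.1 and the templates).* A table built from the remaining study file omits the subject's events. The withdrew-consent row of Template Table 1 could hold the surviving count, but that table is by site, not by arm.
3. *Missing data (12.2).* The weighted GEE and mixture-model analyses estimate a treatment effect and so need each subject's arm. For an expunged subject only the existence of a withdrawal is known. What remains is to bound the result by assigning the expunged subjects to either arm with either outcome.

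**Size.** The plan has no figure on expungement to reproduce. Section 12.1 supplies N = 1200 per group, a control risk p = 20% and a target difference of 5 points. The number expunged, k, and the event risk among them, r, are assumptions. Suppose the true risk is 20% in both arms, only intervention subjects are expunged, and other attrition is ignored. Then

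observed intervention risk = (N·p − k·r) / (N − k), and false benefit = 20% − observed risk.

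| k (share of arm) | r | Observed risk | False benefit |
|---|---|---|---|
| 24 (2%) | 40% | (240 − 9.6)/1176 = 19.6% | 0.4 points |
| 60 (5%) | 40% | (240 − 24)/1140 = 18.9% | 1.1 points |
| 6 (0.5%) | 100% | 234/1194 = 19.6% | 0.4 points |
| 12 (1%) | 100% | 228/1188 = 19.2% | 0.8 points |
| 24 (2%) | 100% | 216/1176 = 18.4% | 1.6 points |
| 60 (5%) | 100% | 180/1140 = 15.8% | 4.2 points |

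The 100% rows are a worst case in which everyone expunged had a repeat ED visit. If r equals 20%, the false benefit is zero for any k. With no true effect, it is also zero if k and r are the same in both arms.

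For scale, the standard error of the difference at 1200 per arm is √(2 × 0.20 × 0.80 / 1200) = 1.6 points.

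**Power.** For 20% against 15%, two-sided 5%, the normal approximation is power = Φ{[0.05√n − 1.96√(2 × 0.175 × 0.825)] / √(0.20 × 0.80 + 0.15 × 0.85)}. After 25% attrition, n = 900 gives 79.8%. Losing a further 0.5% of each arm (n = 896) gives 79.6%, and losing 5% (n = 855) gives 77.7%. Loss of power is not the issue.

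**The case against.** Several limits on the concern are sound.

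- *Notified events are not lost everywhere.* A reader might infer that SAEs already reported disappear. They do not. SAEs go to the NIA and the safety officer within 1 business day, related ones go to the NIH and the IRB within 24 hours (section 8.4), and monthly reports already issued stay with their recipients. Section 7 governs the study's records and recalls nothing. The documents also do not say that cumulative tables are rebuilt each month from the remaining records, so falling counts are a consequence of literal reading, not a stated procedure.
- *Halting does not rest on cumulative counts.* The Appendix A stopping rule is triggered by a single unexpected, related SAE, and no interim analysis is planned (Appendix A, 2.0). A later expungement cannot undo a review already made.
- *The subject count survives.* Because the consent form and note are kept, it would be too strong to say that nothing can be done analytically. Bounds are possible.
- *The intent-to-treat sentence is about adherence.* It does not address subjects who revoke use of their data. This softens the conflict without removing it, because no other text says how such subjects are handled.
- *Erasure may be a deliberate protection* for older adults, some enrolled by proxy. The consent forms are not in the reviewed copy, so what subjects were promised cannot be seen.
- *The lesser level of withdrawal limits the problem.* With permission, those subjects stay under chart review and their primary outcome can still be obtained.

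What stands is the absence of any exemption for arm and safety records, and the resulting mismatch with the by-arm reporting and analysis the plan requires.

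**Conclusion.** The point holds as a gap in the withdrawal rule that is cheap to close. Followed as written, section 7 removes arm and event records from the study file. Later by-arm tables and SAE listings may then be incomplete or may not reconcile with earlier notices. Expunged subjects cannot be counted by arm, kept in the intent-to-treat set, or handled by the planned missing-data methods by arm.

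A reader might also infer that the primary comparison is materially and irrecoverably biased. The documents do not support that. They give no expungement rate, and the 0.4-1.1 point illustration rests wholly on assumed one-sided requests and a doubled event risk. Even then it is smaller than the 1.6-point standard error. The 4.2-point figure needs 60 expunged subjects, all in one arm and all with events. Bias is probably small unless requests differ by both arm and outcome, but under the present rule the trial could not show whether they did.

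**What to change.** Amend section 7 and the matching consent wording, for subjects enrolled from then on, as follows.

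- Full withdrawal stops all contact and all new data collection.
- The study keeps, under the study code with identifiers removed: site, allocated arm, randomisation and withdrawal dates, outcome status up to the withdrawal date, and every adverse event, SAE and unanticipated problem record.
- Withdrawals are reported by arm as well as by site, and these subjects' events stay in the cumulative tables and listings.

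The auto-generated codes and removal of identifiers in section 10 already provide the means. The cost is a protocol and consent amendment. The real downside is that subjects can no longer have coded data already collected erased, and the consent form must say so.

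The change will not recover 30-day outcomes not yet collected at withdrawal. Those come from the Day 30 survey and the chart review at the end of the study (Table 2 and section 6.3). They would be handled as missing data with the arm known, which the methods in section 12.2 require.

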8. SAFETY AND REPORTABLE EVENTS

The level of risk in this supportive care behavioral intervention is low, and no published literature regarding this widely implemented intervention has reported any problems. All research team members will be involved in safety monitoring.

8.1 UNANTICIPATED PROBLEM DEFINITION

An unanticipated problem is an event that includes any symptom, illness, or experience, which develops or worsens during the course of the study and that changes the subject risk/benefit ratio and that is directly related to subjects' participation in the study.

8.2 RECORDING UNANTICIPATED PROBLEMS

During the study follow up calls, research staff will assess if any unanticipated problems have occurred. All unanticipated problems whether observed by the staff, elicited from or volunteered by the subject, will be documented. Each unanticipated problem will include the date of onset, brief description of the experience, the relationship to CTI and any action taken with respect to the CTI.

8.3 SERIOUS ADVERSE EVENT

A serious adverse event is defined as any adverse medical experience that results in any of the following outcomes: 1) death; 2) is life-threatening; 3) requires inpatient hospitalization; 4) results in persistent or significant disability/incapacity; 5) requires medical or surgical intervention to prevent permanent impairment or damage.

8.4 RESPONSIBILITIES FOR REPORTING SERIOUS ADVERSE EVENTS

Any negative reactions that arise during the course of this study will be discussed in the weekly research team meetings. All adverse events will be reviewed to determine if a change in protocol is necessary.

If a serious adverse event related to study activities occurs, it will be reported to the NIH and the University of Wisconsin IRB within 24 hours. If the event took place at the University of Rochester site, it will also be reported to the University of Rochester IRB as well as the University of Wisconsin IRB.

9. RISK/BENEFIT ASSESSMENT

9.1 POTENTIAL RISKS

One risk involves any stress caused by the survey questions or assessments, either through the questions themselves or frustration or fatigue from completing the questions. This risk is moderate, because the questions are standard questions asked by health care providers. However, the risk can be mitigated and made less likely by taking appropriate steps described in the "Protection Against Risk" section.

Another risk involves the release of confidential information regarding the medical conditions for which subjects will be assessed and from the medical record reviews. Release of information can cause social or psychological harm. However, the risk for this is extremely unlikely due to the procedures used to mitigate this issue that are described in the "Protection Against Risk" section.

A third risk is that the study team may be able to identify issues of depression or suicidal thoughts from the surveys. Identification of these issues would require contacting appropriate individuals for intervention (e.g., your ED provider, your health care team).

A fourth risk is identification of abuse or neglect. Home visits will occur as part of this study and child abuse or neglect may be observed during a visit. We are required by state law to report this to the appropriate authorities. This may include reporting to local law enforcement or protective service agencies, resulting in legal or social risks to subjects or other members of their household.

In home visit situations where the paramedic coach identifies that a home environment requires mandatory reporting to authorities the paramedic coach will report as mandated and also communicate their findings to the study Principal Investigator (PI). Additionally, in situations where it is unclear whether mandatory reporting requirements are triggered the paramedic coach will communicate their findings to the study Principal Investigator to further discuss the case. If deemed necessary the research team will communicate concerns to the patient's primary care physician for appropriate follow-up by the PCP.

A final risk is that we may refer subjects to their primary care providers or an ED for additional care. Following these referrals will be dependent upon the subject inclination to accept the referral.

9.2 PROTECTION AGAINST RISKS

Stress: The risk from the stress of the questions will be mitigated by requesting consent to ask the questions, by asking the questions at times of their choosing, and offering to terminate the screening at any point that subjects request.

Release of Confidential Information: To prevent the unintentional release of confidential information for any of the human subjects included in the research study, all data will be stored in locked offices. All electronic data will be stored on secure networked computers / networked drives, as per policy. Only investigators and research staff directly involved in the project will be given access. All identifiers will be stripped from the database at the earliest possible time. For patient data, identifiers will be eliminated upon completion of follow up and data abstraction.

Different Levels of Care: In terms of the acute event, that will be protected against in two ways. First, the ED staff will have completed its primary medical care before consent is requested or assessment is performed. Thus, participation cannot impact ED medical care. Second, in the ED, participation cannot harm medical care because the research staff operates independently of the ED physician. Participation can benefit medical care only from the standpoint that new needs may be identified and addressed, thus improving the health of the older adult.

Depression or Self Harm: To mitigate this risk, we will contact appropriate others to intervene (e.g., the ED provider, their health care team).

Elder or child abuse or neglect: If either abuse or neglect is observed during the coach's' home visit, we are required by state law to and will report this to the appropriate authorities.

Referral to PCP or ED: If needed from a clinical standpoint, the subject may be referred to their PCP or an ED. It will be up to the subject to decide if they wish to act up on this referral.

